### **8.1.1.1 Adverse Events Grading**

All AEs (laboratory and clinical symptoms) will be graded for severity and assessed for relationship to study product (see definitions). AEs characterized as intermittent require documentation of onset and duration of each episode. The start and stop date of each reported AE will be recorded on the appropriate eCRF.

#### **Severity of Event:**

AEs will be assessed by the investigator using the protocol-defined grading system specified in [Section 8.1.2](#) and [Appendix C](#). For events not included in the protocol-defined grading system, the following guidelines will be used to quantify severity:

- Mild (Grade 1): Events that are usually transient and may require only minimal or no treatment or therapeutic intervention and generally do not interfere with the subject's usual activities of daily living.
- Moderate (Grade 2): Events that are usually alleviated with additional specific therapeutic intervention. The event interferes with usual activities of daily living, causing discomfort but poses no significant or permanent risk of harm to the research participant.
- Severe (Grade 3): Events interrupt usual activities of daily living, or significantly affects clinical status, or may require intensive therapeutic intervention. Severe events are usually incapacitating.

---

**Relationship to Study Product:** The assessment of the relationship of an AE to the administration of study product is made only by those with the training and authority to make a diagnosis and listed on the Form FDA 1572 as an investigator based on all available information at the time of the completion of the eCRF. Whether the AE is related or not, is not a factor in determining what is or is not reported in this trial. If there is any doubt as to whether a clinical observation is an AE, the event should be reported.

In a clinical trial, the study product must always be suspect. The relationship to study product will be assessed for AEs using the terms related or not related:

- Related – There is a reasonable possibility that the study product caused the AE. Reasonable possibility means that there is evidence to suggest a causal relationship between the study product and the AE.
- Not Related – There is not a reasonable possibility that the administration of the study product caused the event.

### 8.1.2 Reactogenicity

Reactogenicity events are AEs that are known to occur with this type of study vaccine. The following Toxicity Grading Scales will be used to grade solicited local (injection site) and systemic (subjective and quantitative) reactions:

**Table 3: Injection Site Reactogenicity Grading**

Local (Injection Site) Reaction	Mild (Grade 1)	Moderate (Grade 2)	Severe (Grade 3)
Pain – experienced without touching the injection site (spontaneous discomfort)	Subject is aware of pain but it does not interfere with daily activity and no pain medication is taken	Subject is aware of pain; there is interference with daily activity or it requires use of pain medication	Subject is aware of pain and it prevents daily activity
Tenderness – hurts only when injection site is touched or the arm is moved	The area immediately surrounding the injection site hurts only when touched or with arm motion, and it does not interfere with daily activity	The area immediately surrounding the injection site hurts when touched or with arm motion, and it interferes with daily activity	The area immediately surrounding the injection site hurts when touched or with arm motion, and it prevents daily activity
Pruritus (itching)	Does not interfere with daily activity	Interferes with daily activity	Prevents daily activity
Swelling*	Does not interfere with daily activity	Interferes with daily activity	Prevents daily activity

\* Will be also measured in cm but size will not be used as halting criteria.

**Table 4: Injection Site Reactogenicity Measurements**

Local (Injection Site) Reaction	Small (Grade 1)	Medium (Grade 2)	Large (Grade 3)
Erythema (Redness)*	2.5 – 5 cm	5.1 – 10 cm	> 10 cm
Induration (Hardness)/Swelling*	2.5 – 5 cm	5.1 – 10 cm	> 10 cm

\* Will not be used as halting criteria.

**Table 5: Subjective Systemic Reactogenicity Grading**

Systemic (Subjective)	Mild (Grade 1)	Moderate (Grade 2)	Severe (Grade 3)
Chills	No interference with daily activity	Some interference with daily activity	Significant interference, prevents daily activity
Myalgia (Body Aches/Muscular Pain)*	No interference with daily activity	Some interference with daily activity	Significant interference, prevents daily activity
Arthralgia (Joint Pain)*	No interference with daily activity	Some interference with daily activity	Significant interference, prevents daily activity
Nausea	No interference with daily activity	Some interference with daily activity	Significant interference, prevents daily activity
Vomiting	No interference with daily activity	Some interference with daily activity	Significant interference, prevents daily activity
Headache	No interference with daily activity	Some interference with daily activity	Significant interference, prevents daily activity
Malaise	No interference with daily activity	Some interference with daily activity	Significant interference, prevents daily activity
Fatigue	No interference with daily activity	Some interference with daily activity	Significant interference, prevents daily activity

\* Not at injection site

Oral temperature# will be graded as follows:

**Table 6: Quantitative Systemic Reactogenicity Grading**

Systemic (Quantitative)	Mild (Grade 1)	Moderate (Grade 2)	Severe (Grade 3)
Fever* - oral †	38.0°C – 38.4°C 100.4°F – 101.1°F	38.5°C – 38.9°C 101.2°F – 102.0°F	>38.9°C >102.0°F

# Oral temperature assessed on Day 1 (Visit 01) before the first study product injection will be considered as baseline.

\*Note: A fever can be considered not related to the study product if an alternative etiology can be documented.

† Subjects must not eat or drink anything hot or cold, or smoke within 10 minutes before taking oral temperature.

### **8.1.3 Serious Adverse Events (SAEs)**

An AE or suspected adverse reaction is considered an SAE if, in the view of either the site principal investigator or sponsor, it results in any of the following outcomes:

- death,
- a life-threatening AE\*,
- inpatient hospitalization or prolongation of existing hospitalization,
- a persistent or significant incapacity or substantial disruption of the ability to conduct normal life functions, or
- a congenital anomaly/birth defect.
- important medical events that may not result in death, be life-threatening, or require hospitalizations may be considered serious when, based upon appropriate medical judgment they may jeopardize the patient or subject and may require medical or surgical intervention to prevent one of the outcomes listed in this definition. Examples of such medical events include allergic bronchospasm requiring intensive treatment in an emergency room or at home, blood dyscrasias or convulsions that do not result in inpatient hospitalization, or the development of drug dependency or drug abuse.

\*Life-threatening AE. An AE is considered “life-threatening” if, in the view of either the site principal investigator or sponsor, its occurrence places the patient or subject at immediate risk of death. It does not include an AE that, had it occurred in a more severe form, might have caused death.

SAEs will be:

- Assessed for severity and relationship to study product and alternate etiology (if not related to study product) by a licensed study physician listed on the Form FDA 1572 or by the Institution as the site Principal Investigator or Sub-Investigator.
- Recorded on the appropriate SAE data collection form and eCRF.
- Followed through resolution by a licensed study physician (for Investigational New Drug Application [IND] studies, a physician listed on the Form FDA 1572 as the site PI or Sub-Investigator).
- Reviewed and evaluated by DMID, the DSMB or SMC (periodic review unless related), and the IRB/IEC.

## **8.2 Specification of Safety Parameters**

Safety will be assessed by the frequency and severity of:

### **8.2.1 Solicited Events**

Solicited events are AEs that are common and known to occur following administration of study product.

### **8.2.2 Unsolicited Events**

Unsolicited events are any other AEs that occur following administration of study product.

### **8.2.3 New-Onset Chronic Medical Conditions (NOCMCs)**

NOCMCs are defined as any new ICD-10 diagnosis that is applied to the subject during the duration of the study, after receipt of the study agent, that is expected to continue for at least 3 months and requires continued health care intervention.

### **8.2.4 Medically-Attended Adverse Events (MAAEs)**

Defined as a hospitalization, ER visit, or an otherwise unscheduled visit to or from medical personnel for any reason; and considered related to study product.

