## 3.3 Study Endpoints or Outcome Measures

### 3.3.1 Primary

- Occurrence of study vaccine-related SAEs from the time of the first study vaccination through approximately 12 months after the last study vaccination.
- Occurrence of solicited injection site and systemic reactogenicity events from the time of each study vaccination through 7 days after each study vaccination.
- Occurrence of clinical safety laboratory AEs from the time of each study vaccination through approximately 28 days after each study vaccination.
- Occurrence of all unsolicited AEs, regardless of the assessment of seriousness or relatedness, from the time of each study vaccination through 28 days after each study vaccination.
- Occurrence of SAEs, MAAEs, NOCMCs, and PIMMCs from the time of the first study vaccination through approximately 12 months after the last study vaccination.

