### **7.1.1 Assessment of Concomitant Medications/Treatments other than Study Product**

Administration of any medications, therapies, or vaccines will be recorded on the appropriate eCRF. Concomitant medications will include all current medications and medications taken in the 60 days prior to the first vaccination and those taken from the time of vaccination through approximately 28 days after each vaccination, as described in [Section 3.1](#). Medications reported in the electronic case report form (eCRF) are limited to those taken within 30 days prior to the first study product injection and those taken in the 28-day post-vaccination interval. Prescription and over-the-counter drugs will be included as well as herbals, vitamins, and supplements. In addition, receipt of non-study vaccines will be solicited from the time of each vaccination through approximately 28 days after each vaccination and reported in the eCRF. Use of a new medication should prompt evaluation for the occurrence of any MAAE, including a NOCMC.

Medications that might interfere with the evaluation of the investigational product(s) should not be used during the trial-reporting period (approximately 12 months after the last study vaccination) unless clinically indicated as part of the subject's health care. Medications in this category include the prohibited medications per the Subject Exclusion Criteria (see [Section 5.1.2](#)). In addition, the site PI or appropriate sub-investigator may identify other medications that should not be used due to a risk to subject safety or assessment of reactogenicity and immunogenicity.

---

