## 8 ASSESSMENT OF SAFETY

### 8.1 Assessing and Recording Safety Parameters

Safety will be assessed by the frequency and severity of:

1. SAEs occurring from the time of the first study product injection through the end of follow-up which is approximately 12 months after the last study product injection.
2. Solicited AEs – reactogenicity events occurring from the time of each study product injection through 7 days after each study product injection:
  - a) Injection site reactions including pruritus, erythema, induration/swelling, pain, and tenderness.
  - b) Systemic reactions including fever, chills, fatigue, malaise, myalgia, arthralgia, headache, nausea, and vomiting.
3. Clinical safety laboratory AEs assessed as described in [Section 7.2.1](#). Parameters to be evaluated include WBC, hemoglobin, platelets, ALT, and creatinine.
4. Unsolicited AEs – non-serious AEs occurring from the time of each study product injection through 28 days after the study product injection.
5. MAAEs, NOCMCs, and PIMMCs occurring from the time of the first study product injection through the end of follow-up which is approximately 12 months after the last study product injection.

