3.2. Study Endpoints or Outcome Measures

3.2.1. Primary

- Occurrence of study vaccine-related SAEs from the time of the first study vaccination through approximately 12 months after the last study vaccination
- Occurrence of solicited injection site and systemic reactogenicity events from the time of each study vaccination through 7 days after each study vaccination
- Occurrence of clinical safety laboratory AEs from the time of each study vaccination through approximately 28 days after each study vaccination
- Occurrence of all unsolicited AEs, regardless of the assessment of seriousness or relatedness, from the time of each study vaccination through 28 days after each study vaccination
- Occurrence of SAEs, MAAEs, NOCMCs, and PIMMCs from the time of the first study vaccination through approximately 12 months after the last study vaccination

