4.5.1. Safety Variables

Serious adverse events (SAEs) will be assessed from the time of the first study product injection through the end of the follow-up which is approximately 12 months after the last study product injection.

Solicited adverse events (AEs) will document reactogenicity events occurring from the time of each study product injection through 7 days after each study product injection. Injection site reactions of interest include pruritus, erythema, induration/swelling, pain, and tenderness. Systemic reactions of interest include fever, chills, fatigue malaise, myalgia, arthralgia, headache, nausea, and vomiting.

Unsolicited AEs will document non-serious AEs occurring from the time of each study product injection through 28 days after the study product injection.

Clinical safety laboratory AEs will be collected on the day of and prior to each study product injection, approximately 7 days after each study product injection, and approximately 28 days after each study product injection (which may also serve as the clinical safety laboratory samples for the second and/or third study product injection). Parameters to be evaluated include white blood cells (WBC), hemoglobin, platelets, alanine aminotransferase (ALT), and creatinine.

MAAEs, NOCMCs, and PIMMCs will be assessed from the time of the first study product injection through the end of the follow-up period, which is approximately 12 months after the last study product injection.

All solicited and unsolicited AEs and laboratory values are graded on a scale of 0 (absent), 1 (mild), 2 (moderate), and 3 (severe) according to toxicity grading scales ([Table 6](#), [Table 7](#)).

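### The only MAAE definition admits related events alone, against the protocol's own reporting rule, so late unrelated medical visits go uncollected for an unqualified primary endpoint

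*Protocol*

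**What the plan says.** Protocol 8.2.4 defines an MAAE as a hospitalization, an emergency room visit, or "an otherwise unscheduled visit to or from medical personnel for any reason; and considered related to study product". The sentence first admits visits whatever their cause and then narrows to those attributed to the product. The SAP gives no definition of its own.

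Protocol 8.1.1.1, under relationship to study product, states: "Whether the AE is related or not, is not a factor in determining what is or is not reported in this trial".

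The fifth primary endpoint in Protocol 3.3.1 begins "Occurrence of SAEs, MAAEs, NOCMCs, and PIMMCs from the time of the first study vaccination" and runs to about 12 months after the last dose. SAP 3.2.1 repeats it: "Occurrence of SAEs, MAAEs, NOCMCs, and PIMMCs from the time of the first study vaccination through approximately 12 months after the last study vaccination". Neither attaches a relatedness condition. The first endpoint in the same list does, for SAEs: "Occurrence of study vaccine-related SAEs from the time of the first study vaccination". Two further lists name MAAEs unqualified: Protocol 8.1, item 5 ("MAAEs, NOCMCs, and PIMMCs occurring from the time of the first study product injection through the end of follow-up") and SAP 4.5.1 ("MAAEs, NOCMCs, and PIMMCs will be assessed from the time of the first study product injection through the end of the follow-up period").

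Protocol 3.1 and footnote 3 to Tables 8 and 9 limit collection outside the 28-day windows to SAEs, MAAEs, NOCMCs and PIMMCs.

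**The concern.** For most of follow-up, the MAAE category is the only route by which an ordinary non-serious medical visit reaches the database. If the category is limited to related events, a judgement of unrelated removes the event from collection instead of merely labelling it. Under 8.1.1.1 an investigator makes that judgement, and under Protocol 10.3.2 investigators know the treatment.

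MAAE occurrence is part of a primary endpoint in a first-in-human trial. An event screened out at collection cannot be reassessed later if a pattern appears across subjects.

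The reported tables would not reliably show which reading was used. SAP Table 18 has one MAAE row with no indication of related or all-cause, whereas SAEs have an all-SAE row and a related-SAE row. SAP Table 56 has columns for MAAE status and relationship. One unrelated MAAE there would show that all-cause counting was used, but a list containing only related MAAEs would settle nothing.

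**Working it through.** The plan states no figure for MAAEs, so there is none to reproduce. The check compares the texts and then measures how much follow-up is affected.

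**Texts side by side**

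- *8.2.4 against 8.1.1.1.* Outside the windows, 8.2.4 makes relatedness decide whether a non-serious visit is collected. 8.1.1.1 says it decides nothing of the kind. Both cannot be followed there.
- *8.2.4 against 7.1.1.* The concomitant-medication text (repeated in SAP 4.4.7) reads "Use of a new medication should prompt evaluation for the occurrence of any MAAE, including a NOCMC", which treats a NOCMC as a kind of MAAE. The NOCMC definition in 8.2.3 has no relatedness condition.
- *Weaker support.* Protocol 10.5.2 asks for relationship in the MAAE listing, but that listing also covers NOCMCs, PIMMCs and SAEs. Protocol 8.1.1 and 8.5 require AEs to be recorded or reported whatever the relationship, but may apply only to events already within collection scope.

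**What falls out**

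- Inside a 28-day window the event is still an unsolicited AE (fourth primary endpoint); only its MAAE label is affected.
- Outside the windows it is lost only if it is judged unrelated and is not an SAE, NOCMC or PIMMC.

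**Length of the restricted period**

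Inputs are nominal days from Protocol Tables 8 and 9. Follow-up is counted from Day 2.

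- Groups A, B, D and E: restricted Days 86–422, so 422 − 85 = 337. Follow-up is 422 − 1 = 421. 337/421 = 80.0%.
- Group C: restricted Days 58–179 (122 days) and 209–545 (337 days), total 459. Day 180 is excluded because full collection resumes at the third dose. Follow-up is 545 − 1 = 544. 459/544 = 84.4%.
- All 45 subjects: 36 × 337 + 9 × 459 = 12,132 + 4,131 = 16,263 restricted subject-days. Total 36 × 421 + 9 × 544 = 15,156 + 4,896 = 20,052. 16,263/20,052 = 81.1%. 16,263/365.25 = 44.5 person-years.

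Counting Day 1 as follow-up gives 16,263/20,097 = 80.9%. Moving the boundary visits to the edges of their windows gives 320/407 = 78.6% to 354/435 = 81.4% for Groups A, B, D and E, and 439/530 = 82.8% to 479/558 = 85.8% for Group C.

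**Events**

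The documents give no rate for non-serious, unrelated visits that are neither NOCMCs nor PIMMCs. Purely as an assumption, 0.1 to 1.0 per person-year gives 0.1 × 44.5 = 4.5 to 1.0 × 44.5 = 44.5 events.

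**Possible trace in source records**

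The interim history (Protocol 7.1) might note such a visit. In the restricted period it is taken twice in Groups A, B, D and E (Days 181 and 422) and three times in Group C (Days 180, 304 and 545). Recall gaps are 181 − 85 = 96 and 422 − 181 = 241 days, and for Group C 180 − 57 = 123, 304 − 208 = 96 and 545 − 304 = 241 days.

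**The case against.** The best defence is that MAAE is a defined term. The endpoint lists then carry the definition without repeating it, and the contrast with the vaccine-related SAE endpoint proves little: the SAE definition has no relatedness element, so that endpoint had to add one. The 8.1.1.1 sentence sits in a grading section and may govern only events already in scope. Related-only MAAE collection is also a possible design choice, and the events lost form a narrow class. Inpatient hospitalizations and important medical events are SAEs under 8.1.3, and SAEs, NOCMCs and PIMMCs are collected whatever the relatedness. Sites must also learn of a visit before judging it, and the MOP and eCRF instructions, which might resolve the matter, are not available here.

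Much of this stands as a limit on size. The unqualified lists show a poor fit, not a contradiction, and actual loss depends on instructions not seen. It does not remove the problem. The 8.1.1.1 sentence speaks of what is reported in the trial and states no exception, while 8.2.4 makes relatedness the deciding factor. If related-only was deliberate, the exception has to be written down and the endpoint and Table 18 labelled. If sites record unrelated visits anyway, they depart from 8.2.4, and the count depends on local practice.

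**Conclusion.** The concern holds. Section 8.2.4 as written conflicts with 8.1.1.1 and, through the collection limits, keeps some late medically attended events out of a primary endpoint that states no such restriction. The affected calendar exposure is about four fifths of planned follow-up: 81.1%, or 44.5 person-years across 45 subjects, assuming nominal visit days and complete follow-up. The number of events is unknown, and the 4.5 to 44.5 range rests wholly on an assumed rate.

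This should be corrected, but its reach is limited. The analysis is descriptive, and no halting rule, hypothesis test or sample-size figure depends on MAAEs. Confidence is high about the wording and its literal effect, and lower about how many events would actually go unrecorded.

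**What to change.** Reconcile Protocol 8.2.4, 8.1.1.1 and 3.3.1 with SAP 3.2.1.

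- **Preferred.** Delete the relatedness clause from 8.2.4 and align the eCRF instructions. Keep relatedness as a recorded attribute of each MAAE, and give all MAAEs and related MAAEs separate rows in SAP Table 18, as is done for SAEs. Table 56 needs no change. This follows the rule already in 8.1.1.1 and keeps the data for either summary.
- **Alternative, if related-only was intended.** Say related MAAEs in the fifth endpoint of both documents and in the Table 18 row, and state the exception in 8.1.1.1.

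The preferred change costs one protocol clause, one eCRF instruction and one table row, plus IRB approval of the amendment (Protocol 9.1). Medical history is already reviewed at every scheduled contact, so no visit is added; some extra unrelated MAAE records must be entered and coded. If follow-up has begun, record the date of the change or re-ascertain earlier visits, so that sequentially enrolled groups are not counted under different definitions.

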### **8.2.5 Potentially Immune-Mediated Medical Conditions (PIMMCs)**

PIMMCs constitute a group of AEs that includes diseases which are clearly autoimmune in etiology and other inflammatory and/or neurologic disorders which may or may not have autoimmune etiologies. PIMMCs currently in effect are presented in [Appendix B List of PIMMCs](#).

